5.7.1.2. Sub-group Analyses

To assess the homogeneity of the treatment effect across various subgroups, treatment-by-subgroup factor, time point-by-subgroup factor and treatment-by time point-by subgroup factor interaction terms and a subgroup factor term will be added in the primary

MMRM model. LS mean difference versus placebo at week 24 will be provided, as well as the corresponding SE and 95% CI, within each subgroup. The significance level of the treatment-by-subgroup factor interaction term at week 24 will be also provided for each factor for descriptive purpose. Forest plots will be provided. In order to handle imbalances between randomization stratification factors levels, population weights will be used as for the primary analysis model.

The following subgroups of interest will be evaluated, assuming there are enough patients in each subgroup level to perform the evaluation. For the subgroup factors that are also randomization stratification factors, the IVRS strata will be used.

- The baseline apheresis status (Yes, No) per IVRS,
- Geographical region (Japan, Rest of World) per IVRS,
- Gender (Female, Male),
- Age (<65, ≥65),
- Race
- Ethnicity
- Baseline LDL-C (<130, ≥130 mg/dL),
- HoFH genotyping (homozygous, compound heterozygous, and double heterozygous)
- Receptor-negative mutation in both LDLR alleles (i.e. receptor-negative defined as a mutation resulting in termination codons, splice site mutations, frame shifts and large insertion/deletions) (Yes, No)

Subgroup analysis for Japanese patients

With respect to the subgroup analysis for Japan, the primary efficacy analysis MMRM model will be used to evaluate treatment effect in Japanese patients (as recorded in the electronic data capture [EDC] system) by adding the variables of treatment-by-region strata and treatment-by-time point-by-region strata interaction terms to the model. With this subgroup specific MMRM model, the primary efficacy endpoint LS mean at week 24 for the evinacumab treatment group will be provided for the Japanese patients, along with the corresponding SE and 95% CI. Due to the few Japanese patients expected to be randomized to the placebo group, the evinacumab group LS mean point estimate will be used to assess consistency of evinacumab effect between the Japanese patients and all evinacumab treated patients in this global study (provided by the primary efficacy analysis described in Section 5.7.1). The evinacumab primary efficacy endpoint LS mean point estimate for the Japanese patients is considered to show consistent efficacy results with the global study point estimate when the ratio of the Japanese LS mean point estimate over the global study point estimate is ≥ 0.5 .

5.7.2. Analysis of Secondary Efficacy Variables

Statistical analyses for the key secondary efficacy endpoints (defined in Section 4.7.2) and other secondary efficacy endpoints (described in Section 4.7.3) will be performed in the ITT population using the ITT estimand.

For descriptive summaries, percent change, and when appropriate, absolute change from baseline in LDL-C, Apo B, total-C, TG, non-HDL-C, Lp(a), and Apo CIII will be provided at each time point for each treatment group. All measurements, scheduled or unscheduled, will be assigned to efficacy analysis windows defined in Appendix 10.2 in order to provide an assessment for these time points. For TGs, measurements on not-fasting patients will be excluded. The time profile of each parameter will be plotted by treatment group with the corresponding standard errors. Similar tables (with either percent change from baseline or absolute change from baseline for the ratio) and plots will be provided for other efficacy parameters: Apo A-1 and ratio Apo B/Apo A-1.

Multiple types of measurements are planned to be analyzed during differing time points in the trial, specifically continuous measurements expected to have a normal distribution (example: percent change in LDL-C), continuous measurements expected to have a non-normal distribution (example: TG), and binary measurements (example: proportion of patients with at least 30% reduction in LDL-C).

5.7.2.1. Continuous Endpoints Anticipated to have a Normal Distribution

Continuous secondary variables defined in Section 4.7.2 and 4.7.3 anticipated to have a normal distribution (i.e. lipids other than TG and Lp(a)) will be analyzed using the same MMRM model as described for the primary endpoint. Specifically, the model will contain the fixed categorical effects of treatment group, randomization strata (as per IVRS/IWRS), planned time points up to week 24, strata-by-time point, and treatment-by-time point interaction, as well as, the continuous fixed covariates of corresponding baseline value and baseline value-by-time point interaction.

5.7.2.2. Continuous Endpoints Anticipated to have a Non-normal Distribution

Continuous secondary efficacy variables defined in Section 4.7.2 and 4.7.3 anticipated to have a non-normal distribution (i.e. TG and Lp(a)) will be analyzed using the multiple imputation approach for handling of missing values as described in Appendix 10.7, with data log-transformed before imputation process and then back transformed to create the imputed data sets using the TRANSFORM statement of SAS MI procedure.

The percent change from baseline at time point of interest will be derived from observed and imputed lipid values at this time point. Multiple imputation will be followed by robust regression model (Mehrotra 2012) to compare treatment group differences, with the endpoint of interest as the response variable using M-estimation (using SAS ROBUSTREG procedure) with treatment group, randomization strata (as per IVRS/IWRS) and corresponding baseline value(s). Combined means estimates for both treatment groups, as well as the differences of these estimates, with their corresponding SEs, 95% CIs and p-value will be provided through the SAS MIANALYZE procedure.

5.7.2.3. Binary Endpoint Variables

Binary secondary efficacy endpoints defined in Section 4.7.2 and 4.7.3 will be analyzed using the multiple imputation approach for handling of missing values as described in Appendix 10.7.

The binary endpoint at time point of interest will be derived from observed and imputed lipid values at this time point. Multiple imputation will be followed by stratified logistic regression,

(with strata defined as randomized in the IVRS/IWRS) using the strata option of the SAS logistic procedure. The logistic regression procedure will be used to compare treatment group differences, with the model containing treatment group and corresponding baseline value(s) as covariate, stratified by randomization strata defined as per IVRS/IWRS. Combined estimates of odds ratio versus placebo, 95% CI, and p-value will be obtained through the SAS MIANALYZE procedure.

In the data dependent case such logistic regression is not applicable (e.g. the response rate is zero in one treatment arm and thus the maximum likelihood estimate may not exist), the last observation carried forward (LOCF) approach would be used for handling of missing values. Treatment effects would be compared using the stratified exact conditional logistic regression method, specifically using the strata option of the SAS logistic procedure (with strata defined as randomized in the IVRS/IWRS). In case the model would not converge with stratification variables, an unstratified exact logistic regression will be performed. The LOCF imputation method will consist of using the last value obtained up to the week 24 efficacy analysis window to impute the missing week 24 value.

In case of computing issues with exact logistic regression, the baseline level(s) will be entered in the model as a categorical variable(s) using quartiles. Exact odds ratio versus placebo, 95% CI, and p-value will be provided.

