Continuous secondary efficacy endpoints defined in Section 4.2.2 and Section 4.2.3 anticipated to have a non-normal distribution (ie, TG and Lp[a]), will be analyzed using a robust regression model (ie, ROBUSTREG SAS procedure with M-estimation option) with treatment group and randomization stratum as main effect and corresponding baseline value(s) as a covariate. Missing values will be addressed using a multiple imputation approach, which will be described in the SAP. The variables in the multiple imputation model will at least include the same variables as used in the robust regression model. The treatment group combined means will be provided with respective SE estimates. The combined mean difference between the treatment groups will be provided with the SE, 95% confidence interval (CI) and p-value.

III. Binary endpoints

Binary secondary efficacy endpoints defined in Section 4.2.2 and Section 4.2.3 will be analyzed using stratified logistic regression (using the strata option of the SAS logistic procedure) with treatment group and randomization stratum as main effect and corresponding baseline value(s) as a covariate. Missing values will be addressed using a multiple imputation approach, which will be described in the SAP. The variables in the multiple imputation model will at least include the same variables as used in the logistic regression model. Treatment effects will be compared and the combined odds ratio estimate between the treatment groups, with their corresponding 95% CI and p-value will be provided.

In the data dependent case that the logistic regression method is not applicable (eg, the response rate is zero in one treatment arm and thus the maximum likelihood estimate may not exist), the last observation carried forward (LOCF) approach would be used for handling of missing values and an exact conditional logistic regression would be performed to compare treatment effects. The LOCF imputation method will consist of using the last value obtained up to the week 24 time window to impute the missing week 24 value.

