6.3. Premature Withdrawal from the Study

A patient has the right to withdraw from the study at any time, for any reason, and without repercussion.

The investigator and/or sponsor have the right to withdraw a patient from the study if it is no longer in the interest of the patient to continue in the study, or if the patient's continuation in the study places the scientific outcome of the study at risk (eg, if a patient does not or cannot follow study procedures). An excessive rate of withdrawals would render the study uninterpretable; therefore, unnecessary withdrawal of patients should be avoided.

Patients who are withdrawn prematurely from the study will be asked to complete study assessments, as described in Section 8.1.5.

Rules for discontinuation of study treatment (permanent or temporary) are discussed in Section 7.4.2.

Early Termination from the Study

If for any reason the patient withdraws from the study prematurely, the patient should undergo an unscheduled visit with assessments normally planned at the end of the double-blind treatment visit if the patient is in the DBTP, or the end of the open-label treatment visit, if the patient is in the OLTP. The visit should take place within 5 days of treatment discontinuation. The assessments completed should include pregnancy testing for WOCBP. The patient should be followed for at least 24 weeks from the last dose of study drug or up to recovery or stabilization of any AE to be followed-up as specified in this protocol, whichever comes last. A final end of study visit should take place with assessments as specified in the end of study visit (ie, follow up visit) at 24 weeks after the premature discontinuation of study drug.

Sexually active WOCBP who discontinue the study prematurely should be reminded at the unscheduled visit following treatment discontinuation to maintain highly effective contraceptive measures for 24 weeks after the last dose of study drug. At this visit, the patient will be provided 5 urine pregnancy tests with instructions to test for pregnancy 4 weeks after this visit and Q4W thereafter. The patient will also be notified of Q4W follow-up phone calls to confirm continued contraception use and pregnancy reporting and to obtain the results of the urine pregnancy test.

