Continuous secondary efficacy endpoints defined in Section 4.2.2 and Section 4.2.3 anticipated to have a non-normal distribution (ie, TG and Lp[a]), will be analyzed using a robust regression model (ie, ROBUSTREG SAS procedure with M-estimation option) with treatment group and randomization stratum as main effect and corresponding baseline value(s) as a covariate. Missing values will be addressed using a multiple imputation approach, which will be described in the SAP. The variables in the multiple imputation model will at least include the same variables as used in the robust regression model. The treatment group combined means will be provided with respective SE estimates. The combined mean difference between the treatment groups will be provided with the SE, 95% confidence interval (CI) and p-value.

III. Binary endpoints

Binary secondary efficacy endpoints defined in Section 4.2.2 and Section 4.2.3 will be analyzed using stratified logistic regression (using the strata option of the SAS logistic procedure) with treatment group and randomization stratum as main effect and corresponding baseline value(s) as a covariate. Missing values will be addressed using a multiple imputation approach, which will

be described in the SAP. The variables in the multiple imputation model will at least include the same variables as used in the logistic regression model. Treatment effects will be compared and the combined odds ratio estimate between the treatment groups, with their corresponding 95% CI and p-value will be provided.

In the data dependent case that the logistic regression method is not applicable (eg, the response rate is zero in one treatment arm and thus the maximum likelihood estimate may not exist), the last observation carried forward (LOCF) approach would be used for handling of missing values and an exact conditional logistic regression would be performed to compare treatment effects. The LOCF imputation method will consist of using the last value obtained up to the week 24 time window to impute the missing week 24 value.

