- Patients who stopped taking their study treatment no longer benefited from it after discontinuation, and thus tended to have LDL-C values returning to baseline. Therefore, LDL-C values missing after the on-treatment period should be imputed based on patient’s own baseline value.

Missing data from the randomized population will be imputed 100 times to generate 100 complete data sets, using the SAS MI procedure (using Markov Chain Monte Carlo). The 100 completed datasets of observed and imputed LDL-C data will be used for the sensitivity analysis of the primary efficacy analysis method.

For the percent change from baseline calculated LDL-C endpoint, the 100 complete datasets of observed and imputed LDL-C data at week 24 will be analyzed using an ANCOVA model with treatment group and randomization strata as fixed effect, and the baseline LDL-C value as continuous covariate. The SAS MIANALYZE procedure will be used to generate valid statistical inferences by combining results from the 100 analyses using Rubin’s formulae.

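### When the responder model cannot be fitted, the plan also swaps multiple imputation for LOCF, so the missing-data rule of an alpha-controlled test depends on the observed responder counts

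*SAP*

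**What the plan says.** SAP 5.7.2.3 states that the binary secondary endpoints "will be analyzed using the multiple imputation approach for handling of missing values as described in Appendix 10.7". Stratified logistic regression is then fitted in each imputed data set and the results are combined.

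The same section has a fallback for when that regression is not applicable. Its example is that "the response rate is zero in one treatment arm and thus the maximum likelihood estimate may not exist". In that case the analysis becomes exact conditional logistic regression, and "the last observation carried forward (LOCF) approach would be used for handling of missing values". LOCF is defined as "using the last value obtained up to the week 24 efficacy analysis window to impute the missing week 24 value". Protocol 10.4.3.2 has the same fallback: "The LOCF imputation method will consist of using the last value obtained up to the week 24 time window".

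Five of the nine key secondary endpoints in SAP 4.7.2 are binary, and all nine are tested in a fixed sequence (SAP 5.7.2.5). The only sensitivity analysis planned for the key secondaries is the on-treatment one in the mITT population (SAP 5.7.2.4). The pattern mixture model of SAP 5.7.1.1 and Appendix 10.8 covers the primary endpoint only.

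**The concern.** The fallback makes two changes when one is needed. A zero responder count is a problem of the likelihood: the maximum likelihood odds ratio does not exist. It carries no information about why week-24 values are missing, so it cannot justify a different assumption about them.

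Two consequences follow. First, whether a confirmatory test rests on multiple imputation or on LOCF is decided by the responder counts. Second, LOCF is a single imputation. It enters an earlier value as if it were the observed week-24 result, and the between-imputation variance that Rubin's rules would carry is lost.

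The ≥50% reduction endpoint is fifth of nine in the sequence, so a result obtained under the fallback also decides whether the four endpoints below it are tested. No planned analysis would show what the switch did.

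**Working it through.** **Inputs.** From SAP 2.2: 38 evinacumab and 19 placebo patients, difference 38 percentage points, common SD 35, two-sided alpha 0.05, 5% non-evaluable and 15% dropout. The documents give no placebo mean change. I assume 0 and normality, and vary the SD.

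**1. The plan's own figure.** A two-sample t-test with 2:1 allocation has power 0.899 with 14 + 28 evaluable patients and 0.919 with 15 + 30. Inflating the 45: 45 / 0.80 = 56.25, or 45 / (0.95 × 0.85) = 55.7. Rounding up by arm gives 19 + 38 = 57, as stated. The plan gives no figure for the binary endpoints.

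**2. Chance of the trigger.** The probability that a patient reaches a reduction of at least c is Φ((−c − μ)/σ). The chance of no responder among n patients is (1 − p)^n.

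- ≥50%, placebo: p = Φ(−50/35) = 0.0766; 0.9234^19 = 0.220. With 15 placebo patients observed, 0.9234^15 = 0.303.
- ≥30%, placebo: p = Φ(−30/35) = 0.1957; 0.8043^19 = 0.016.
- ≥50%, evinacumab: p = Φ((−50 + 38)/35) = 0.366; the chance of 0/38 is negligible. The text covers either arm, but placebo is the likely one.

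| SD | P(0/19), ≥50% | P(0/19), ≥30% |
|---|---|---|
| 35 | 0.22 | 0.016 |
| 30 | 0.39 | 0.038 |
| 25 | 0.65 | 0.098 |
| 20 | 0.89 | 0.27 |

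The other three binary key secondaries depend on absolute LDL-C at week 24. The plan gives no baseline distribution, so I have not computed them.

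**3. How many values would be taken as known.** If 15% to 20% lack a week-24 value, that is 38 × 0.15 = 5.7 to 38 × 0.20 = 7.6 evinacumab patients, and 19 × 0.15 = 2.9 to 19 × 0.20 = 3.8 placebo patients. The upper figure adds the 5% non-evaluable to the 15% dropout. The documents do not show that those 5% are leavers, so 20% is a high value.

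**4. Expected shift from multiple imputation to LOCF.** The imputation in Appendix 10.7 uses treatment, baseline, visit values and a few covariates. It assumes missing at random and has no return-to-baseline step. If carried-forward values respond at the completers' rate, both methods credit missing evinacumab patients with about 0.366 responders each. The expected shift is then 38 × m × (0.366 − 0.366) = 0 for any missing fraction m. What changes is the stated precision.

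**5. Why precision can still matter.** With Fisher's exact test standing in for the exact regression, 8/38 against 0/19 gives p = 0.042 and 7/38 gives p = 0.083. Near that boundary, one carried-forward value counted as certain can decide the test.

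**The case against.** **The fallback is pre-specified and has a practical reason.** Exact conditional p-values do not combine directly by Rubin's rules, so pairing an exact test with one completed data set is understandable. This stands in part. The rule is written in advance, but which branch applies is settled by the outcome data, and a penalised-likelihood model removes the need for an exact test.

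**The point estimate hardly moves.** This stands in full. A reader might infer that LOCF tilts responder rates toward evinacumab, because the SAP says of the primary endpoint that "Patients who stopped taking their study treatment no longer benefited from it after discontinuation, and thus tended to have LDL-C values returning to baseline". Against return to baseline, LOCF would credit 38 × 0.15 × (0.366 − 0.077) = 1.65 to 38 × 0.20 × (0.366 − 0.077) = 2.20 more evinacumab responders, or 4 to 6 percentage points. The documents do not support reading that as the effect of the switch:

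- LOCF replaces the missing-at-random imputation of Appendix 10.7. Return to baseline is never planned for the binary endpoints.
- The rule carries the last value obtained, on drug or off. Protocol 7.4.2 asks patients who stop drug to keep attending all double-blind visits, so many would have off-drug values. A carried on-drug value is typical only of those who leave the study on stopping drug, for whom "The visit should take place within 5 days of treatment discontinuation" (Protocol 6.3).
- The pattern mixture model itself assumes missing at random up to 35 days after the last dose. Week 24 is day 169 and the week-20 dose is day 141. The gap is 28 days, so a patient who misses week 24 after that dose is not returned to baseline there either.

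**The effect on decisions is small.** With no placebo responders and the plan's effect, the chance of p < 0.05 is 0.988 under LOCF, against 0.940 (15% missing) or 0.906 (20% missing) if missing patients count as non-responders. Multiplied by the 22% trigger, this is 0.22 × 0.048 = 0.011 to 0.22 × 0.082 = 0.018 of trials. The gap is wider at a true response rate of 30% (0.921 against 0.789 or 0.724), but non-response is a harsher comparator than the planned imputation. Inflation of type I error is not shown: with no drug effect, on-drug and off-drug values do not differ.

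**Conclusion.** The point holds in a limited form. Whenever logistic regression is not applicable, SAP 5.7.2.3 and Protocol 10.4.3.2 change the missing-data method as well as the model, without a reason that bears on missingness. An alpha-controlled key secondary test may then rest on a single imputation that ignores uncertainty, and the responder counts decide whether it does.

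The trigger is realistic for one endpoint: about 22% for ≥50% reduction at the plan's SD, higher if the SD is smaller, and about 1.6% for ≥30%. These figures rest on normality, zero mean placebo change and 19 placebo patients. The expected change in responder rates relative to the planned imputation is near zero if leavers' last values respond at the completers' rate. The loss of precision is not quantified here; it grows with the number of missing week-24 values. No directional bias toward evinacumab is established, and the recommendation does not depend on one.

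**What to change.** In SAP 5.7.2.3, replace the LOCF fallback. Keep the 100 imputed data sets of Appendix 10.7, fit Firth penalised-likelihood logistic regression in each with treatment, randomization strata and baseline value, and combine the estimates with Rubin's rules. One missing-data rule then applies in both branches. Because Protocol 10.4.3.2 also names LOCF, record the change in the table of modifications in SAP 1.2.4.

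Counting missing values as goal not met should not be the main fix, since it again changes the missing-data rule only in the fallback. It can serve with an exact test as a supportive analysis. For the two apheresis-eligibility endpoints, the unfavourable outcome must then be defined as meeting the criterion.

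The cost is a few lines of SAP text and code, made before the first-step database lock, up to which the SAP allows revision. The downside is small: strata enter as fixed effects instead of being conditioned out, and the p-value is no longer exact. Firth regression on these data sets keeps the missing-at-random assumption. It restores consistency and imputation uncertainty, and does not test that assumption.
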